5 STUDY ENROLLMENT AND WITHDRAWAL

5.1 Participant Enrolment Inclusion Criteria

This pragmatic clinical trial is designed to evaluate a "real-world" setting, requiring a broad study population. In order to be eligible, study participants must meet the following criteria:

- 1. Adults (> 18 years old) who are > 3 months after starting chronic HD;
- 2. No expected change in dialysis modality or relocation outside of Winnipeg during the intervention period (12 weeks);
- 3. Assessed to be safe and able to exercise by the HD unit nephrologist¹;
- 4. Able to understand and provide written informed consent

5.2 Participant Enrolment Exclusion Criteria

Individuals meeting any of the following criteria will be excluded from participation:

- 1. Acute coronary syndrome in the past 3 months;
- 2. Unstable arrhythmia;
- 3. Shortness of breath at rest or with minimal activity (NYHA Class 4);
- 4. Symptomatic hypoglycemia (>2x/week in week prior to enrolment);
- 5. Currently participating in the Manitoba Renal Program's clinical intradialytic cycling program;
- 6. Score of '0' on Dialysis Symptom Index when administered at time of consent;

5.3 Strategies for Recruitment and Retention

A total of **150** chronic adult hemodialysis patients will be randomized at the 4 Winnipeg HD units over 2 years or until the target enrolment has been achieved. Approximately 325 individuals commence chronic HD in Winnipeg per year. At any time, there are approximately 700 prevalent patients receiving in-centre HD in Winnipeg. Assuming eligibility rate of 40% and a conservative 25% enrolment rate (based on previous studies and pilot data), the targeted sample size is achievable over the proposed 2-year study period and would amount to a maximum of 5 patients cycling per shift at each of the 4 HD units involved in the study at any one time. Based on our clinical cycling program experience (where we have up to 10 individuals cycling per shift), this rate of enrolment is easily achievable.

_

¹ Nephrologists will be provided with verbal instructions and written guidelines to loosely follow when assessing for safety to exercise

Recruitment feasibility: We anticipate meeting the target enrolment within the study period given: a) the size of the target in-centre hemodialysis population outlined above and; b) we have selected a minimal number of clinically relevant inclusion criteria based on input from clinicians and clinical trialists (Canadian Nephrology Trials Network, CNTN)⁷⁵ to maximize study eligibility and participant generalizability.

Recruitment organization: Posters and study information brochures may be used to facilitate recruitment. All recruitment materials will have been reviewed and approved by the REB prior to use.

Recruitment management: Enrollment progress will be evaluated monthly, and in the event that enrollment targets are not met per the recruitment schedule, the recruitment of an additional study site (Calgary: co-PI [name]) will be considered.

Recruitment retention: Participants will be reimbursed for travel to study appointments at a rate of \$20 per round trip for each study appointment attended.

5.4 Participant Withdrawal or Termination

5.4.1 Reasons for Withdrawal or Termination

Participants will complete the study after their 12-month study visit is complete. Participants are free to withdraw from participation in the study at any time, for any reason, specified or unspecified without penalty. Participants may also be withdrawn from the study if, in the opinion of the Investigator, it is in their best interests to do so. Participants may also be withdrawn from the study for any of the following reasons:

- 1. The participant is "lost to follow-up" (i.e. no further follow-up is possible because attempts to re-establish contact with the subject have failed);
- 2. The participant meets an exclusion criteria, either newly developed or not previously recognized, that precludes further study participation;
- 3. Any clinical adverse event (AE), laboratory abnormality, or other medical condition or situation occurs such that continued participation in the study would not be in the best interest of the participant;
- 4. Death.

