2.3 Potential Risks and Benefits

2.3.1 Known Potential Risks

The risks associated with study participation will be fully disclosed to participants. Occurrence of events will be monitored at every study visit, and will constitute grounds for termination of study intervention in study patients – these participants will remain in the study on a strictly observational basis.

Risk of Disclosure of Personal Health Information: There is a potential risk of disclosure of personal health information with any clinical study and database. All study personnel have undergone ethics, GCP CITI training, and taken a Pledge of Confidentiality (PHIA).

A secure study database will be maintained for the trial purposes. The study database will utilize appropriate security measures to protect patient privacy and data. All study participant information will be entered using a unique study identifier. All data and samples will be analyzed using the study identifier with no personal health information linked to it. Each Site Principal Investigator will hold the key to the de-identified information in a locked and secure office. The Subject Identification Code List that links the identity of the participant with subject ID for de-identified data will be maintained with the trial's master file, according to ICH-GCP, Section 8.3.

Risk of Exercise: Participation in this trial of monitored exercise is low risk. Multiple previous studies of intradialytic exercise in individuals with ESKD have demonstrated no significant adverse events with such interventions. However, it should be noted that none of these studies were powered for safety outcomes. Participants will be carefully pre-screened for safety to exercise by the attending HD unit nephrologists and study staff and the program of exercise will be modified for each individual's personal health status and gradually incremental in intensity and duration. However, there is a certain degree of risk involved in the initiation of any exercise program. Patients will be monitored for the following risks:

- Muscle or joint soreness following initiation of an exercise program
- Low blood pressure on hemodialysis after exercising
- Develop chest pain (angina) during or after exercise
- Develop an irregular/fast heart rhythm (arrhythmia) during or after exercise
- Develop an acute coronary syndrome during or after exercise
- Develop hypoglycemia during or after exercise in setting of diabetes on medications

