7 STUDY SPECIFIC PROCEDURES

7.1 Study Procedures/Evaluations

The study-specific procedures and time-points to be done over the course of the study are summarized below and in Section 7.3 of the protocol:

Enrolled Study Population (both study groups)

- Informed Consent (enrolment, visit 0)
- Final study eligibility assessment including administration of DSI (enrolment, visit 0)
- Randomization (baseline)
- Collect Baseline Demographics age; gender; ethnicity/race (baseline, visit 1)
- Collect Past Medical History cause of end stage renal disease; diabetes; hypertension; smoking; cardiac disease/arrythmia; cerebrovascular disease/stroke/transient ischemic attack; lung disease; peripheral vascular disease/lower extremity amputation; arthritis; date of dialysis start; other relevant medical history (baseline, visit 1)
- Collect Concomitant Medications (each study visit)
- Collect vital signs/clinical data height, weight, BMI, systolic and diastolic blood pressure; dialysis adequacy (Kt/V); weekly intradialytic fluid gains; duration of HD and heart rate (each study visit; height will only be done on the 1st baseline visit)
- Collect Clinical Laboratory results (each study visit):
 - o Blood: hemoglobin, calcium, albumin, phosphate
- Patient compliance with the study protocol will be monitored in accordance to the Monitoring Plan (each study visit)
- Dialysis Symptom Index (enrolment visit and each study visit)
- EQ-5D-5L (each study visit)
- Time required for recovery following hemodialysis (each study visit)
- Download 7 day accelerometry history (each study visit)
- Godin-Shephard Leisure-Time Exercise Questionnaire (each study visit)
- Incremental Shuttle Walk Test (each study visit)
- Frailty status using the Modified Fried Criteria (each study visit)
- Self-Efficacy for Exercise Survey (each study visit)
- Cause and length of any hospitalization since last study visit (study visit 2, 3 and 4)
- Death (study visit 2, 3 and 4)

 Physical activity/exercise logs (collected weekly for first 12 weeks then every 2 weeks for next 40 weeks)

Intervention Group – Additional Evaluation

 Maximal incremental cycle test to volitional exhaustion⁷⁸ (After randomized to intervention and before intervention started)

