8.4.2 Serious Adverse Event Reporting

The PI is responsible for the detection and documentation of events meeting the criteria and definition of a serious adverse event (SAE). Serious adverse events will be collected from the time of the randomization until the study completion, or until 30 days after the subject prematurely withdraws from the study.

After learning that a participant has experienced an SAE, the PI is responsible for reporting the SAE as per REB's guidelines. The SAE report will be completed within 7 working days of the reported event. The DSMB may request to receive real-time notification of all SAEs thought to be related to the treatment procedure. At the time of the event, as much information as possible must be collected, but at a minimum must include the following:

- AE description
- Relationship to study exercise intervention.
- Relationship to protocol mandated procedures
- Reason why the event is serious.
- Supplementary CRF pages that are current at the time of SAE reporting: medical history, concomitant medications, demographics, death.

All SAEs will be followed until satisfactory resolution or until the site PI deems the event to be chronic or the adherence to be stable. As additional details become available, the SAE CRF should be updated and submitted to the site's ethics committee.

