Appendix 2. Study Definitions

Early discontinuation	The study participant will be considered an "early discontinuation" in the event that they withdraw from the study during the initial 6 months of the study (withdrawal of consent, adverse effects etc.).
Intent-to-Treat sample	All randomized participants who receive the exercise intervention/standard-of-care
Lost to Follow-up	Study participants may be considered "lost to follow up" after the subject misses a minimum of 2 consecutive study visits, and the site personnel has made a number of unsuccessful phone contacts. The decision to early terminate the subject will be the decision of the PI, all attempts to establish contact with the subject will be documented in the study files.
Protocol Mandated Procedures	Any procedure performed solely for the purpose of this research study (not site-specific standard of care)
Randomized	A participant who has met all eligibility criteria; met with the study investigator or designee to discuss the study purpose, requirements (i.e. time requirements, schedule of events etc), discussed all the risks and benefits; signed the informed consent document and was randomly assigned to one of the two study groups.
Study Intervention	The investigational regimen and all protocol required therapies. This includes standardized lifestyle education, 26 weeks of cycling during HD and 26 weeks of home-based resistance exercises.
Terminated	A participant will be terminated prematurely from the study if: 1) Participant withdraws consent; Lost to follow-up, or; death.

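### Section 5.4.1 allows withdrawal from the study after randomisation for events that section 2.3.1 says end only the intervention, which can lose 12-week outcomes and safety follow-up, possibly unequally by arm

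*Combined protocol and SAP*

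**What the plan says.** Three places in the protocol govern what happens to a randomised participant who has a serious event or turns out to meet an exclusion criterion.

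- **Section 5.4.1** lists reasons for withdrawal from the study, not just from exercise. Item 2 reads "The participant meets an exclusion criteria, either newly developed or not previously recognized, that precludes further study participation". Item 3 covers an adverse event, laboratory abnormality or other condition that "occurs such that continued participation in the study would not be in the best interest of the participant". A general sentence before the list also allows withdrawal whenever the investigator judges it to be in the participant's best interests.
- **Section 2.3.1** says that the listed events are grounds for ending the study intervention, and that "these participants will remain in the study on a strictly observational basis". One listed event is "Develop an acute coronary syndrome during or after exercise"; arrhythmia is another. These two overlap exclusion criteria 1 and 2 in section 5.2.
- **Appendix 2**, under 'Terminated', says: "A participant will be terminated prematurely from the study if: 1) Participant withdraws consent; Lost to follow-up, or; death". Its 'Early discontinuation' entry, however, gives adverse effects as an example of a reason for withdrawal.

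For data after withdrawal, section 5.4.2 asks for an exit visit and/or final outcome assessments and promises every effort to obtain final data. Section 8.4.2 collects serious adverse events (SAEs) until study completion "or until 30 days after the subject prematurely withdraws from the study". Section 9.3.1 analyses available cases by intention to treat and uses multiple imputation only if more than 25% of outcomes are missing.

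**The concern.** If an event that may be caused by the intervention can also end follow-up, the set of people with a 12-week outcome depends on what happened after randomisation. An available-case comparison is then exposed to loss that is related to outcome and may differ between arms.

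The same rule can remove people from the safety record. SAE collection stops 30 days after withdrawal, hospitalisation is ascertained at the scheduled assessments, and mortality is a 1-year proportion. The people whose follow-up is cut short could be those with the cardiac events that the trial is monitoring.

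**Working it through.** **1. One event under each rule.** Take an exercise-arm participant who has an acute coronary syndrome before week 12.

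- Section 2.3.1: the intervention ends and the participant stays under observation.
- Section 5.4.1 item 2 (exclusion 1 has newly developed) or item 3 (adverse event): the participant may be withdrawn from the study.
- Appendix 2 'Terminated': the event is not a listed reason.
- Appendix 2 'Early discontinuation': withdrawal for adverse effects is foreseen.

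Site staff could keep or withdraw this person, and either choice follows some part of the protocol.

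**2. What is lost if 5.4.1 is followed.** Section 7.2 sets the assessment at 12 weeks within 10 days either side. Section 5.4.2 does not require that assessment, and it does not say whether an earlier exit DSI counts as the 12-week value. Without a 12-week DSI, the participant leaves the primary comparison.

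Imputation need not follow. Losing 15 of the 75 exercise participants and no controls is 15/150 = 10% missing, below the 25% trigger. Section 9.2 anticipates 30% dropout, so total loss could pass the trigger, but the imputation then assumes missing at random.

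**3. Why the loss may be unequal.** Most events in 2.3.1 are worded as occurring during or after exercise. The maximal cycle test is done only in the intervention arm, "After randomized to intervention and before intervention started" (section 7.1), so it could bring to light a criterion that had not been recognised. Appendix 2 defines the intention-to-treat sample as "All randomized participants who receive the exercise intervention/standard-of-care". Read literally, someone withdrawn between that test and the start of the programme might fall outside it.

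**4. The plan's own figure.** Inputs from section 9.2: response 50% v 25%, power 80%, alpha 0.05. With two-sided testing and pooled variance:

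n = [1.960 × √(2 × 0.375 × 0.625) + 0.842 × √(0.50 × 0.50 + 0.25 × 0.75)]² / 0.25² = 57.7, so 58 per arm.

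This reproduces the stated 58. Retaining withdrawn participants does not change it.

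**5. Worst-case size.** Assumptions: 75 per arm randomised; k exercise-arm non-responders removed; no controls removed; everyone else assessed. For true exercise-arm response p, the expected observed response is p × 75/(75 − k), and the control rate stays at 25%. For example, with k = 4 and p = 0.25, 18.75/71 = 26.4%, a shift of 1.4 points. Type I error comes from 400,000 simulated trials using a two-sided pooled z (chi-square) test at 0.05.

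| k removed (share of 75) | Spurious difference, 25% true in both arms | Type I error | Apparent difference if truth is 50% v 25% |
|---|---|---|---|
| 0 | 0 | 0.050 | 25.0 points |
| 4 (about 5%) | 1.4 points | 0.056 | 27.8 points |
| 8 (about 10%) | 3.0 points | 0.068 | 31.0 points |
| 11 (about 15%) | 4.3 points | 0.086 | 33.6 points |
| 15 (20%) | 6.3 points | 0.136 | 37.5 points |

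The test level follows section 9.2. Section 9.3.3 gives two-sided p < 0.01 for all analyses; that would change the type I error column but not the shifts in points.

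**6. When the bias vanishes.** If removal is unrelated to outcome, there is no expected bias. Power falls slightly, from 89.3% with 75 per arm to 87.6% with 8 removed from one arm. Removing equal shares of non-responders from both arms gives no bias when the true rates are equal.

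**The case against.** The strongest reply is that the texts can be read together. Section 5.4.1 says that participants may be withdrawn, and item 2 is limited to criteria that preclude further participation. Section 2.3.1 is the specific rule for exercise harms and keeps those people in. Section 5.4.2 promises every effort to obtain final outcomes. Section 9.3.1 adds a sensitivity analysis for the missing-at-random assumption, 9.3.4 compares completers with non-completers, and 9.3.5 reports reasons for discontinuation. Hospitalisation comes partly from chart review, cause of death comes from dialysis unit records, and SAEs already reported are followed to resolution.

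Much of this stands and limits the size of the problem. It does not say which rule governs a given event, make the 12-week DSI mandatory, or extend SAE collection beyond 30 days.

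A reader might also infer more than the documents support:

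- **That hypoglycemia is a third overlapping criterion.** Exclusion 4 refers to the week before enrolment, so it cannot newly develop after randomisation.
- **That using the clinical cycling programme (exclusion 5) triggers withdrawal.** Section 7.4.3 permits it after the intervention phase in either arm, so it does not explain a 12-week imbalance.
- **That unrecognised exclusions are sought in one arm only.** The cycle test serves to standardise intensity (7.4.2). Both arms do the shuttle walk test, whose checklist in the appendices covers rest angina, pulse and hypoglycaemic episodes. Both arms also have the same adverse event questioning and chart review (5.5.2).
- **That 20% is an expected loss.** The same percentage appears as a stopping level in section 5.5, but that level also counts access complications and tendon rupture. It does not estimate removals under 5.4.1.

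**Conclusion.** The conflict between 5.4.1, 2.3.1 and Appendix 2 is in the text and should be resolved. Following 5.4.1 can lose 12-week outcomes and safety follow-up in people with intervention-related events, and the loss may be greater in the exercise arm.

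It would go too far to say that the rule does bias the trial toward exercise, or that it removes mainly exercise-arm patients with poor outcomes. The documents give no expected number, no arm split and no link between removal and DSI response.

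The range of 1.4 to 6.3 points, with type I error 0.056 to 0.136, rests on the worst-case assumptions in step 5 and on assumed removal of 5% to 20% of one arm. At 5% or less the effect is small. An exit DSI accepted as the outcome would reduce it further. The possible loss of SAE, hospitalisation and mortality follow-up does not depend on those bias assumptions.

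**What to change.** Reconcile section 5.4.1 (items 2 and 3 and the general investigator-opinion sentence), section 2.3.1 and the Appendix 2 definitions, so that stopping the study intervention is separate from leaving follow-up. The general sentence must be included; otherwise the same withdrawals remain possible under it.

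State that, unless consent is withdrawn or contact is lost, every randomised participant stays in the assigned arm for the scheduled outcomes at Visits 2 to 4, and for SAE collection, hospitalisation and mortality to week 52. This applies the approach that 2.3.1 already takes. The rules on when exercise is stopped are for the sponsor and are left unchanged.

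The cost is one protocol amendment and a few more visits or chart reviews in people already enrolled. It should be made before outcomes are lost, because no analysis can recover outcomes that were never measured.

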5.4.2 Handling of Participant Withdrawals or Termination

Participants who withdraw will not be replaced in the event that the target accrual rate for randomization is obtained. If the overall target accrual rate is lower than expected, or the drop-out rate is higher than expected, than recruitment will continue to reach the target study number.

If there is a reason for medical withdrawal, the participant will remain under the care of their primary dialysis nephrologist. The primary investigator will be available for consultation as needed. The date and reason for withdrawal will be documented in the participant's record. If a participant is prematurely terminated from the study for any reason, they will be asked to complete a final study exit visit and/or final outcome assessments. Every effort will be made to obtain final data collection on treatments and outcomes, to reduce potential sources of bias. Follow-up for unresolved adverse events reported at the time of withdrawal will be the same as outlined in the adverse event section of the protocol.

5.4.3 Participant Suspension from the Study

The site principal investigator may temporarily suspend the study protocol if they judge that the participant's health would be temporarily at risk in continuing the study protocol, such as with the occurrence of an acute illness requiring hospitalization;

Participants should not re-commence the study protocol, until BOTH the attending dialysis nephrologist and the site principal investigator feel that the medical condition has resolved and the participant is safe to resume the protocol.

5.5 Premature Termination or Suspension of the Study

The study may be temporarily suspended or prematurely terminated if there is sufficient reasonable cause. The study PI and the Data Safety Monitoring Board (DMSB) will review safety data on an ongoing basis. Notification of, including written documentation of the reason for study suspension or termination will be provided by the suspending or terminating party to the PI, REB, and regulatory authorities as applicable. Circumstances that may warrant termination of the study or suspension include:

- 1. Determination of unexpected, significant, or unacceptable risk to participants, such as:
 - Severe adverse events related to the exercise intervention, rates above expected (>20% of participants develop new angina, new arrhythmia, myocardial infarction, serious hemodialysis access complications or tendon rupture);
- 2. Across both Intervention and Control Arms, incidence of:
 - Death rates above expected, and attributable to the study protocol.
- 3. Insufficient compliance to protocol requirements.
- 4. Data that is not sufficiently complete and/or evaluable.

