5.5.3 List of Adverse Events to Be Collected for DSMB

Adverse Events:

- 1. Fistula blow
- 2. Muscle aches or pains
- 3. Symptomatic Intradialytic hypotension (BP < 90 mmHg or 20 mmHg drop from baseline associated with symptoms such as headache, cramping, dizziness, nausea)
- 4. Intradialytic cramping
- 5. Increasing fatigue
- 6. Symptomatic hypoglycemia (sugar < 4 associated with typical symptoms of hypoglycemia)
- 7. Fall
- 8. Foot ulcer

Serious Adverse Events:

- 1. Chest pain while exercising (either intradialytic or outside of dialysis)
- 2. Arrhythmia while exercising (either intradialytic or outside of dialysis)
- 3. Unstable hemodialysis necessitating transfer to emergency post hemodialysis
- 4. Tendon rupture
- 5. Fall with fracture
- 6. Admission to hospital for any cause
- 7. Acute coronary syndrome
- 8. Death from any cause

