7.4.2 Intervention Arm, Exercise Rehabilitation Program

Participants will receive exercise counseling as per controls. To standardize intervention exercise intensity, a maximal incremental cycle test (to volitional exhaustion)⁷⁸ will be performed prior to hemodialysis on a mid-week dialysis day on an ergometer in the hemodialysis unit or at the Wellness Institute depending on availability of testing equipment and patient preference. Participants will then participate in a 12-week exercise rehabilitation program as follows (See Section 7.4.5 Study Intervention Schematic):

- 1. Standardized one-on-one lifestyle education sessions at HD provided by the study kinesiologist: Self-management exercise education using Wellness Institute Cardiac Rehabilitation program modules for 1 hr/wk during the first 4 weeks of the intervention. An additional 4 standardized sessions focused on maintenance of lifelong physical activity will be provided over the remaining intervention period.
- 2. Resistance training, using tubing and body weight, based on established guidelines:^{79, 80} Weekly resistance training education will be provided by the study kinesiologist in one-on-one format at HD during the first 4 weeks of intervention. Resistance training bands, instructions and logbooks provided for home exercise (goal 2 sessions/week) during the 26-week intervention period (See Section 7.4.6 Summary Exercise Rehabilitation Program).
- 3. Intradialytic cycling during HD (intensive and maintenance phase): Participants will cycle on TherapyCycleTM (Greely, CO) ergometers modified for dialysis beds or chairs⁸¹ with an initial target exercise intensity of 50-60% of individual maximal workload as determined by the incremental cycling test.^{49,82} Target exercise duration will be 60 minutes in the first half of each HD session, 3 times per week for 12 weeks. Rest periods will be provided as needed if participants are unable to complete 60 minutes of continuous exercise.^{82,83} Duration of total exercise time, average workload (Watts) and self-reported exercise intensity as measured by Borg Rating of Perceived Exertion (RPE) will be recorded by participants for each exercise session. Target Borg RPE will be 13, which is considered to be moderate intensity.⁸⁴ Ergometer resistance will be adjusted over time by the study kinesiologist as triggered by a 1-point change in Borg RPE.

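### The DSMB event list does not line up with the trial's only numeric safety criterion, so that criterion's numerator may be under-ascertained

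*Combined protocol and SAP*

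**What the plan says.** Section 5.5 lists circumstances that may warrant suspending or ending the trial. The only one with a number concerns "Severe adverse events related to the exercise intervention, rates above expected", explained in brackets as ">20% of participants develop new angina, new arrhythmia, myocardial infarction, serious hemodialysis access complications or tendon rupture".

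Section 5.5.3 lists the events to be collected for the DSMB. Among the serious events are "Chest pain while exercising (either intradialytic or outside of dialysis"), "Arrhythmia while exercising (either intradialytic or outside of dialysis"), "Acute coronary syndrome" and "Tendon rupture", together with any hospital admission, emergency transfer after unstable dialysis, and death. The only access event is fistula blow, under the non-serious events.

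Section 5.5.2 gives four routes of ascertainment. Item 1 is a question put to participants at each assessment visit, limited to the events on that list. Items 2 to 4 are chart review, events noted by the kinesiologist or coordinator, and reports from dialysis staff.

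Section 2.3.1, on the risks for which patients will be monitored, is wider than the list. It includes "Develop an irregular/fast heart rhythm (arrhythmia) during or after exercise" and words the angina risk in the same way. Section 7.4.2 places cycling early in the session: "Target exercise duration will be 60 minutes in the first half of each HD session, 3 times per week for 12 weeks".

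**The concern.** A safety criterion is only as good as the capture of its components. Here the one participant question with a stated content and schedule is built on a list narrower than both the criterion and the protocol's own risk section. Cycling takes place in the first half of dialysis, so an arrhythmia later in the same session, or angina that evening, already falls after exercise and is not a listed event in its own right. A serious access complication that needs no admission has no entry under its own name.

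The DSMB would then be weighing a proportion in which some components are actively asked about and others surface only if someone notices and reports them. Incomplete capture moves the count in one direction, downwards. The two arms may also be captured unevenly: controls are asked to refrain from intradialytic cycling during the intervention period (7.4.1), so the intradialytic form of the two cardiac entries will arise mainly in the intervention arm.

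**Working it through.** The plan states no figure to reproduce. The main check sets the criterion's components against the list.

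| Component in 5.5 | Entry in 5.5.3 | Match |
|---|---|---|
| Myocardial infarction | Acute coronary syndrome, no timing limit | Full |
| Tendon rupture | Same | Full |
| New angina | Chest pain, during exercise only | Partial |
| New arrhythmia | Arrhythmia, during exercise only | Partial |
| Serious access complication | Fistula blow, as a non-serious event | No serious entry |

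Two of five match fully, two in part, and one has no serious entry. Any component that leads to admission or emergency transfer is also picked up by those entries.

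**Could an unlisted event belong in the numerator?** Yes, on the plan's own definitions.
- Relatedness: 8.2.2 places possible attribution, used when there is uncertainty, among the related categories. Post-exercise angina can therefore be classed as related.
- Severity: the grade 3 (severe) definition in 8.2.1 describes hospitalization as possible, not required. A severe event without admission can therefore exist.

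An event can thus be severe, related and named in 5.5, yet have no matching prompt in 5.5.3.

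**Denominator.** 5.5 says participants without saying which. With N from 9.2, the smallest count above 20% is floor(0.20 × N) + 1:
- Intervention arm: 0.20 × 75 = 15, so 16 participants.
- All participants: 0.20 × 150 = 30, so 31 participants.

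If every related event arose in the intervention arm, 31 participants would be 31/75 = 41% of that arm, against 16/75 = 21%. The choice of denominator therefore changes what the criterion means.

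**Why partial capture would matter (illustration only).** Let p be the true proportion of participants with a qualifying event and s the share captured. The chance that the observed count passes the criterion is P(X ≥ r), with X ~ Binomial(N, p × s) and r as above. Both p and s are assumed; the documents give neither.

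| N | r | p | s = 100% | s = 80% | s = 60% |
|---|---|---|---|---|---|
| 75 | 16 | 25% | 0.805 | 0.431 | 0.089 |
| 75 | 16 | 30% | 0.965 | 0.746 | 0.267 |
| 150 | 31 | 25% | 0.909 | 0.451 | 0.038 |
| 150 | 31 | 30% | 0.996 | 0.854 | 0.225 |

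The table assumes full enrolment, one look at the data, and equal and independent capture across participants. It shows that the criterion is sensitive to capture. It does not show how much capture is lost in this trial.

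**The case against.** The strongest reply is that the list is not the only route to the DSMB. Items 2 to 4 of 5.5.2 are not worded as limited to it. Section 8.1.1 defines an adverse event broadly, 8.2.3 has all events of grade 2 or higher reported, 8.3 names unsolicited complaints, questioning and nurse or nephrologist reports as sources, and 8.4.1 puts all adverse events on the CRF and has the DSMB review the data. A serious access event needing intervention can meet 8.1.2 without admission, and 8.5 gives the DSMB listings of all SAEs. The kinesiologist also collects logs from controls weekly (7.4.1) and checks in with intervention participants at least weekly in the intensive phase (7.4.2).

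All of this stands, and it rules out several stronger readings.
- A reader might infer that the numerator is not collected, or that the DSMB cannot evaluate the criterion. The routes above, and the admission and transfer entries, contradict that. What is missing is a specified prompt.
- A reader might set 3 × 60 minutes of cycling against a 168-hour week and conclude that 1 − 3/168 = 98% of cardiac symptoms are off the list. That figure is clock time, not events, and it leaves out home exercise. The criterion counts only severe, exercise-related events, so the relevant gap is the period after exercise, and the documents do not size it.
- A reader might infer that the exercise-linked entries can occur in one arm only. Controls may exercise outside the protocol (7.4.1) and the same entries apply to them. Exposure differs; the rule does not.

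It is also fair that 5.5 describes what may warrant action and is not a binding boundary. Treating exercise-related chest pain and arrhythmia as SAEs is a cautious choice open to the sponsor.

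The reply does not remove the conflict between 2.3.1 and 5.5.3 over events after exercise, or the lack of a serious access entry. A symptom at home that needed no admission may never reach a dialysis chart, and attribution can only follow capture.

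**Conclusion.** The point holds as a mismatch between 5.5.3 and both 5.5 and 2.3.1. Three of the five components of the only numeric safety criterion lack a full matching entry in the list that governs the participant question. For post-exercise angina or arrhythmia, and for serious access events, that lead to neither admission nor emergency transfer, capture depends on unprompted routes. The numerator may therefore be too low, by an amount that cannot be derived from the documents. The probabilities in the table rest on assumed event and capture rates and serve only to show direction and sensitivity. Separately, the denominator is undefined, which leaves the trigger at either 16 of 75 or 31 of 150. This is an inconsistency worth correcting; it does not show that safety monitoring is absent.

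**What to change.** Reconcile 5.5.3 with 5.5 and 2.3.1:
- List angina or chest pain, and arrhythmia, in both arms whenever they occur, with a timing field (during exercise, after exercise, other).
- Add an entry for serious hemodialysis access complications, separate from fistula blow.
- State in 5.5 whether the percentage is of the intervention arm or of all participants.
- Reconcile the 5.5.3 classification of exercise-related chest pain and arrhythmia as SAEs with the outcome-based definition in 8.1.2. Whether to keep that classification is for the sponsor, as is the 20% threshold; neither needs to change for this point.

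The cost is a few list and CRF entries and slightly more non-serious cardiac and access events to record. The sample size and the efficacy analyses are unaffected.
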